Plasma concentrations of lemborexant and its metabolites (M4, M9, and M10) will be measured using validated liquid chromatography-tandem mass spectrometry (LC-MS/MS) assay methods.

Statistical Methods

Details of statistical methods and analyses will be specified in the Statistical Analysis Plan (SAP).

The following endpoints will compare lemborexant treatments with placebo:

Primary Endpoint (HV Cohort)

The mean SpO₂ during TST on Day 1 of treatment

Secondary Endpoints (HV Cohort)

1. The AHI on Day 1 of treatment
2. The percentage of TST during which SpO₂ is <90%, <85% and <80% on Day 1 of treatment
3. The proportion of subjects with at least one incident of SpO₂ <90% for at least 30 seconds during TST on Day 1 of treatment

Primary Endpoint (OSA Cohort)

The AHI on Day 8 of treatment

Secondary Endpoints (OSA Cohorts)

1. The AHI on Day 1 of treatment
2. The mean SpO₂ during TST on Day 1 and Day 8 of treatment
3. The percentage of TST during which the SpO₂ is <90%, <85% and <80% on Day 1 and Day 8 of treatment
4. The proportion of subjects with at least one incident of SpO₂ <90% for at least 30 seconds during TST on Day 1 and Day 8 of treatment.

Exploratory Endpoints (HV and OSA Cohorts)

1. The mean SpO₂ during REM sleep, NREM and wake
2. The AHI during REM and NREM sleep
3. The AHI separately for adult and elderly subjects at all days assessed
4. The mean SpO₂ during TST separately for adult and elderly subjects at all days assessed

Pharmacokinetic Endpoint (HV and OSA Cohorts)

Lemborexant and metabolites M4, M9 and M10 plasma concentrations

Pharmacokinetic/Pharmacodynamic (Exposure-Response) Endpoint (HV and OSA Cohorts)

Correlations between plasma concentrations of lemborexant and select pharmacodynamic variables including AHI, mean SpO₂ during TST, and proportion of TST in which SpO₂ is <90%, <85% and <80% at all days assessed.

Analysis Sets

Safety Analysis Set: Group of subjects who received study drug and have at least one postdose safety assessment.

Pharmacodynamic Analysis Set: The PD Analysis Set is the group of subjects who received at least 1

dose of study drug in all Treatment Periods and who had sufficient PD data to derive at least 1 primary PD parameter.

Pharmacokinetic Analysis Set: Group of subjects who have at least 1 quantifiable plasma concentration after dosing with lemborexant.

Efficacy Analyses

Not applicable

Pharmacokinetic Analyses

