3.1.2 Secondary Objectives

Secondary Objectives (HV Cohort)

1. Determine whether lemborexant increases the apnea-hypopnea index (AHI) after a single dose of treatment compared with placebo
2. Determine whether lemborexant decreases SpO₂ during TST below defined thresholds after a single dose of treatment compared with placebo
3. Evaluate safety and tolerability of lemborexant

Secondary Objectives (OSA Cohort)

1. Determine whether lemborexant increases the AHI after the first dose of treatment compared with placebo
2. Determine whether lemborexant decreases the mean SpO₂ during TST after the first and multiple doses of treatment compared with placebo

3. Determine whether lemborexant increases the proportion of TST during which the SpO₂ is decreased below defined thresholds after the first and multiple doses of treatment compared with placebo
4. Evaluate safety and tolerability of lemborexant

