5 STATISTICAL METHODS

All analysis will be reported separately for each cohort. All descriptive statistics for continuous variables will be reported using mean, standard deviation (SD), median, minimum and maximum. Categorical variables will be summarized as number (percentage) of subjects.

All statistical tests will be based on the 5% level of significance (2-sided), unless otherwise stated. If statistical comparisons are not defined, all pairwise comparisons will be tested.

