5.1.2 Secondary Endpoints

Secondary Endpoints (HV Cohort)

1. The AHI on Day 1 of treatment
2. The percentage of TST during which SpO₂ is <90%, <85% and <80% on Day 1 of treatment
3. The proportion of subjects with at least one incident of SpO₂ <90% for at least 30 seconds during TST on Day 1 of treatment

Secondary Endpoints (OSA Cohorts)

1. The AHI on Day 1 of treatment
2. The mean SpO₂ during TST on Day 1 and Day 8 of treatment
3. The percentage of TST during which the SpO₂ is <90%, <85% and <80% on Day 1 and Day 8 of treatment
4. The proportion of subjects with at least one incident of SpO₂ <90% for at least 30 seconds during TST on Day 1 and Day 8 of treatment.

Exploratory Endpoints (HV and OSA Cohorts)

1. The mean SpO₂ during REM sleep, NREM and wake
2. The AHI during REM and NREM sleep
3. The AHI separately for adult and elderly subjects at all days assessed
4. The mean SpO₂ during TST separately for adult and elderly subjects at all days assessed

Pharmacokinetic Endpoint (HV and OSA Cohorts)

Lemborexant and metabolites M4, M9 and M10 plasma concentrations

Pharmacokinetic/Pharmacodynamic (Exposure-Response) Endpoint (HV and OSA Cohorts)

Correlations between plasma concentrations of lemborexant and select pharmacodynamic variables including AHI, mean SpO₂ during TST, and proportion of TST in which SpO₂ is <90%, <85% and <80% at all days assessed.

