5.4.2 Secondary Pharmacodynamic Analyses

Analysis for the Secondary Endpoints

The continuous secondary endpoints for both cohorts will be analyzed using the same model as the primary endpoint. Treatment comparison will be performed using contrasts.

The proportion of subjects with SpO₂ <90% will be summarized using descriptive statistics. All analyses will be performed separately for each cohort.

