13.3 SAS Code Example for Proc Logistic

The following statements use the LOGISTIC procedure to fit a two-way logit with interaction model for the effect of Treatment and AgeGroup, with Age as covariate. The categorical variables Treatment and Sex are declared in the CLASS statement.

```
proc logistic data=XXXX;
class Treatment AgeGroup;
model Binary_Response= Treatment Treatment*AgeGroup AgeGroup / expb;
run;
```

Programming Note: **EXPB option** displays the exponentiated values of the parameter estimates in the “Analysis of Maximum Likelihood Estimates” table for the logit model. These exponentiated values are the estimated odds ratios for the parameters.

SIGNATURE PAGE

Investigational Product Name: E2006/Lemborexant

SIGNATURES	
Authors:	
<hr/> 
PPD [Redacted] PPD [Redacted] [Redacted] Neuroscience Business Group Eisai Inc.
	Date
<hr/> 
PPD [Redacted] PPD [Redacted] [Redacted] Neuroscience Business Group Eisai Inc.
	Date
<hr/> 
PPD [Redacted] PPD [Redacted] [Redacted] Neuroscience Business Group Eisai Inc.
	Date
<hr/> 
PPD [Redacted] PPD [Redacted] [Redacted] Neuroscience Business Group Eisai Inc.
	Date

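### The subject-level SpO₂ <90% endpoint is reported only as percentages by treatment; a within-subject table with a paired difference and 90% CI would use the crossover at little cost.

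*SAP*

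**What the plan says.** The Statistical Methods part of the protocol synopsis introduces its endpoint list with "The following endpoints will compare lemborexant treatments with placebo". The binary desaturation endpoint is on that list as a secondary endpoint in both cohorts. SAP 5.1.2 defines it for the HV cohort as "The proportion of subjects with at least one incident of SpO₂ <90% for at least 30 seconds during TST on Day 1 of treatment". For the OSA cohort it is "at least one incident of SpO₂ <90% for at least 30 seconds during TST on Day 1 and Day 8 of treatment". The related HV objective in SAP 3.1.2 is also comparative: "Determine whether lemborexant decreases SpO₂ during TST below defined thresholds after a single dose of treatment compared with placebo".

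SAP 5.4.2 treats the two kinds of secondary endpoint differently. On one side, "The continuous secondary endpoints for both cohorts will be analyzed using the same model as the primary endpoint", with treatment contrasts. On the other, "The proportion of subjects with SpO₂ <90% will be summarized using descriptive statistics". SAP 5 says what that amounts to: "Categorical variables will be summarized as number (percentage) of subjects". The protocol synopsis and Protocol 9.7.1.7.2 give the binary endpoint the same descriptive treatment.

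The only binary-response model in the SAP is the example code in Appendix 13.3: "model Binary_Response= Treatment Treatment*AgeGroup AgeGroup / expb". No section of the SAP body cites it or links it to an endpoint.

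**The concern.** Both cohorts are crossovers, so each completer gives a yes/no result on placebo and on each lemborexant treatment. The within-subject information lies in the discordant subjects: those who desaturated only on lemborexant and those who desaturated only on placebo. Percentages by treatment drop these counts. The point difference can still be read from the two percentages, but its precision cannot, because the variance of a paired difference depends on the discordant counts. This is the only listed secondary pharmacodynamic endpoint without a within-subject contrast.

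Two other places in the SAP might seem to fill the gap, and neither does. SAP 5 says that where comparisons are not defined, all pairwise comparisons will be tested, but it names no method. The Appendix 13.3 code has treatment, age group and their interaction, with no subject, period or sequence term and no stratification by subject. If it were applied to this endpoint, it would treat a subject's repeated nights as independent.

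At stake is how a safety reader interprets a difference in desaturation rates: as a shift in one direction within the same people, or as movement both ways.

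**Working it through.** **The plan's own figure.** There is none for this endpoint. The documents state power for AHI (OSA) and mean SpO₂ (HV) only, and those figures are not affected here.

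**Inputs from the documents.** 30 OSA completers and 12 HV completers (SAP 4). The primary analyses use a two-sided 90% CI (SAP 5.4.1), and the same level is used below.

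**Assumed inputs.** The documents give no event or discordance rate. For illustration, take OSA margins of 16/30 on lemborexant and 10/30 on placebo. Let b be the number desaturating only on lemborexant and c the number only on placebo, so b - c = 6. Then both = 16 - b and neither = 14 - c.

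**Difference.** d = (b - c)/n = 6/30 = +20 points, whatever the split.

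**Within-subject correlation.** phi = (both × neither - b × c)/√(16 × 14 × 10 × 20), with denominator 211.7. Independence would put 16 × 10/30 = 5.3 subjects in the both cell. Splits with phi ≥ 0 therefore have at least 6 subjects in that cell, which means b from 6 to 10.

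**Paired 90% CI (Tango score).** The interval holds all d with |T(d)| ≤ 1.645, where T(d) = (b - c - nd)/√{n[2p + d(1 - d)]}, p = [√(B² - 4AC) - B]/(2A), A = 2n, B = -b - c + (2n - b + c)d and C = -cd(1 - d).

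| b vs c | Both / neither | phi | 90% CI (points) | Exact McNemar p |
|---|---|---|---|---|
| 6 vs 0 | 10 / 14 | 0.66 | +10.1 to +34.3 | 0.031 |
| 7 vs 1 | 9 / 13 | 0.52 | +5.3 to +35.5 | 0.070 |
| 8 vs 2 | 8 / 12 | 0.38 | +3.0 to +36.7 | 0.109 |
| 10 vs 4 | 6 / 10 | 0.09 | -0.5 to +39.0 | 0.180 |

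The planned table would show 53.3% and 33.3% in every row.

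**Unpaired reading of the same margins.** SE = √(0.533 × 0.467/30 + 0.333 × 0.667/30) = 0.125. The 90% CI is 20 ± 1.645 × 12.5, or -0.6 to +40.6 points (Fisher p = 0.192). This is close to the 10 vs 4 row and much wider than the 6 vs 0 row. If nights within a subject are positively correlated, reading precision from the margins understates what the data show.

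**What a test could add.** If all k discordant subjects go one way, the exact two-sided McNemar p is 2 × 0.5^k. That is 0.0625 for k = 5 and 0.031 for k = 6, so at least 6 are needed for p < 0.05. With assumed discordance of 20 to 40% (lemborexant only) against 0 to 20% (placebo only), power at the two-sided 5% level is about 22 to 57% with 30 subjects and 2 to 7% with 12.

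**The case against.** Descriptive reporting of this endpoint is a consistent choice. The synopsis, Protocol 9.7.1.7.2 and SAP 5.4.2 all say the same, and it is defensible in a Phase 1 safety study with small cohorts and no multiplicity adjustment (SAP 5.3.3). A reader might infer from the synopsis lead-in that the plan contradicts itself. The documents do not support that: the lead-in is general, and percentages side by side are a comparison of a kind.

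A reader might also infer that the threshold objective has no within-subject analysis. That is wrong. Percentage of TST with SpO₂ <90%, <85% and <80% gets the crossover mixed model, and SAP 3.1.2 words the third OSA objective in those terms.

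More extreme splits could be used to widen the contrast, such as 13 vs 7. That leaves 3 subjects in the both cell and gives phi = (3 × 7 - 13 × 7)/211.7 = -0.33. Subjects who desaturate on one night would then be less likely to do so on another, which is hard to defend for repeated measurements.

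The case against a mandatory test or model also stands. Power is low, and HV events should be rare, since Protocol 9.3.2 and 9.3.5 require screening AHI <5 and exclude any valid SpO₂ <90% event at screening. A non-significant result could then be misread as reassurance. McNemar's test ignores period, and logistic regression conditional on subject has no finite estimate at 6 vs 0.

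Individual data will be listed (SAP 5.3.6), so pairs could be tallied afterwards. The table shells are a separate document (SAP 11) and might hold a paired display, but the SAP does not require one. None of this makes marginal percentages the better summary.

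**Conclusion.** The point holds as a cheap improvement to the reporting of one secondary endpoint. As planned, the table omits the discordant counts and gives no valid precision for the difference. In the illustration, identical margins go with a 90% lower bound anywhere from +10.1 to -0.5 points. That range rests on assumed counts, 30 complete pairs and non-negative within-subject correlation; the real event rates may be much lower, above all in the HV cohort.

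It does not follow that the crossover is wasted for desaturation in general, that a hypothesis test is required, or that the Appendix 13.3 code will be used here. That code is uncited; the concern is only that it would be unsuitable for repeated nights if someone applied it. No sample size or primary analysis changes.

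**What to change.** In SAP 5.4.2, for each lemborexant dose and assessment day (HV: 10 mg and 25 mg on Day 1; OSA: 10 mg on Days 1 and 8), report:

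- the within-subject table against placebo: both, lemborexant only, placebo only, neither;
- the paired difference in proportions with a 90% CI, naming the method (for example the Tango score interval), presented as estimation.

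An exact McNemar p-value may be added as supportive, but is not needed. State that this replaces the default pairwise testing in SAP 5 for this endpoint.

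Delete the Appendix 13.3 code, or tie it to a named endpoint with a method that accounts for repeated nights within subject.

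The cost is a few lines of SAP text and one extra table per cohort. No new data are needed, and SAP 3 allows documented changes approved before unblinding.

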5.4.3 Exploratory Analyses

Summaries and plots of all endpoints may be produced for appropriate subgroups (eg age group, sex, BMI, race) as deemed necessary.

5.5 Pharmacokinetic, Pharmacogenomic, and Other Biomarker Analyses

5.5.1 Pharmacokinetic Analyses

The Safety Analysis Set will be used for individual plasma concentration listings of lemborexant and its metabolites M4, M9, and M10. The PK Analysis Set will be used for summaries of plasma concentrations of lemborexant and its metabolites M4, M9, and M10, by dose.

5.5.2 Pharmacogenomic, and Other Biomarker Analyses

DNA samples will be collected and stored, and may be used to examine the role of genetic variability in absorption, distribution, metabolism, and excretion, or development of AEs. Variations in lemborexant exposure or AEs may be explored by correlation of single nucleotide polymorphisms with PK, safety, or PD data.

5.5.3 Pharmacokinetic/Pharmacodynamic (Exposure-Response) Analysis

The exposure-response (E-R) between plasma concentration of lemborexant after PSG, and selected PD parameters including but not limited to the respiratory safety variables, AHI, SpO₂ during TST, and the proportion of TST in which SpO₂ is <90%, <85%, and <80%) will be explored graphically. Any emergent relationship may be followed using population model-based analysis. The potential effects of covariates (eg, age) on the E-R relationship may be explored. The PK analysis set will be used for these assessments. All analyses will be performed separately for each cohort.

5.6 Safety Analyses

Safety analyses will be performed on the Safety Analysis Set unless otherwise specified. Safety data, presented by treatment group, will be summarized on an “as treated” basis using descriptive statistics (eg, n, mean, standard deviation, median, minimum, maximum for continuous variables; n [%] for categorical variables). Safety variables include treatment-emergent adverse events (TEAEs), clinical laboratory parameters, vital signs and 12-lead ECG results. Baseline for all safety analyses is defined as the last predose assessment prior to each periods’ dosing. Extent of Exposure

The extent of exposure (mean daily dose, cumulative dose, duration of exposure) to study drug will be summarized descriptively for lemborexant in the OSA Cohort. For the HV Cohort extent of exposure will be summarized by the number of subjects receiving each treatment.

Compliance for the OSA Cohort for lemborexant will be calculated on the basis of the number of tablets dispensed, lost, and returned, separately for each type (dose) of tablet. Summaries will provide descriptive summary statistics and number (percentage) of subjects below 80%, between 80% and 120%, and greater than 120%.

5.6.1 Adverse Events

The AE verbatim descriptions (investigator terms from the eCRF) will be classified into standardized medical terminology using the Medical Dictionary for Regulatory Activities (MedDRA). Adverse events will be coded to the MedDRA (Version 20.1 or higher) lower level term closest to the verbatim term. The linked MedDRA PT and primary system organ class (SOC) are also captured in the database.

A treatment-emergent adverse event (TEAE) is defined as an AE that emerges during treatment, having been absent at pretreatment (Baseline) or

- Reemerged during treatment, having been present at pretreatment (Baseline) but stopped before treatment, or
- Worsened in severity during treatment relative to the pretreatment state, when the AE is continuous.

Only those AEs that are treatment-emergent will be included in summary tables. All AEs, treatment-emergent or otherwise, will be presented in subject data listings. AEs will be classified as TEAEs up to 14 days after the last study treatment.

An overview of the TEAEs will be summarized by treatment group, including the number and percentage of subjects who experience TEAEs, treatment-related TEAEs, severe TEAEs, TEAEs leading to death and discontinuation from study/study drug.

The incidence of TEAEs will be reported as the number (percentage) of subjects with TEAEs by SOC and PT. A subject will be counted only once within an SOC and PT, even if the subject experienced more than 1 TEAE within a specific SOC and PT. The number (percentage) of subjects with TEAEs will also be summarized by maximum severity (mild, moderate, or severe). The number (percentage) of non-serious TEAEs with an incidence of greater than 5% will be summarized.

The number (percentage) of subjects with TEAEs will also be summarized by relationship to study drug (Yes [related] and No [not related]). Treatment-related TEAEs include those events considered by the investigator to be related to study treatment.

The number (percentage) of subjects with TEAEs leading to death will be summarized by MedDRA SOC and PT for each treatment group. A subject data listing of all AEs leading to death will be provided.

The number (percentage) of subjects with treatment-emergent SAEs will be summarized by MedDRA SOC and PT for each treatment group. A subject data listing of all SAEs will be provided.

The number (percentage) of subjects with TEAEs leading to discontinuation from study drug will be summarized by MedDRA SOC and PT for each treatment. A subject data listing of all AEs leading to discontinuation from study drug will be provided.

The number (percentage) of subjects with TEAEs of cataplexy that are characterized according to the customized MedDRA query PT as potential cataplexy-related events ([Section 9.5.1.5 of the Protocol](#)), or as seizure-related events will be summarized separately. Adjudicated events will also be presented separately.

5.6.2 Laboratory Values

Clinical laboratory values will be evaluated for each laboratory parameter by subject separately for each cohort. Abnormal laboratory values will be identified as those outside (above or below) the normal range. Reference (normal) ranges for laboratory parameters will be included in the clinical study report for this study. Descriptive summary statistics (eg, mean, SD, median, minimum, maximum for continuous variables, and number and percentage for categorical variables) for the laboratory parameters and changes from baseline will be evaluated by treatment group and visit.

Laboratory test results will be assigned a low-normal-high (LNH) classification according to whether the value was below (L), within (N), or above (H) the laboratory parameter's reference range. Within-treatment comparisons will be based on 3 by 3 tables (shift tables) that, for a particular laboratory test, compare the Study Baseline LNH classification to the LNH classification at end of study/early termination, by treatment group.

Clinical laboratory results postbaseline will be evaluated for markedly abnormal values. A laboratory test will be considered markedly abnormal if the result worsens to meet Eisai grading criteria for laboratory values limit of Grade 2 or higher. If the Grade 2 limit is missing, the Grade 1 limit will be considered. [Appendix 13.1](#) presents the Eisai grading criteria for laboratory values that were used to identify subjects with markedly abnormal laboratory values. For the incidence of markedly abnormal laboratory values, each subject may be counted once in the laboratory parameter value high and in the laboratory parameter low categories as applicable.

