9.7.1.8.3 LABORATORY VALUES

Laboratory results will be summarized using Système International (SI) units, as appropriate. For all quantitative parameters listed in [Section 9.5.1.5.3](#), the actual value and the change from baseline to each postbaseline visit and to the end of treatment (defined as the last on-treatment value) will be summarized by visit and treatment using descriptive statistics. Qualitative parameters listed in [Section 9.5.1.5.3](#) will be summarized using frequencies (number and percentage of subjects), and changes from baseline to each postbaseline visit and to end of treatment will be reported using shift tables. Percentages will be based on the number of subjects with both nonmissing baseline and relevant postbaseline results.

Laboratory test results will be assigned a low/normal/high (LNH) classification according to whether the value was below (L), within (N), or above (H) the laboratory parameter's reference range. Within-treatment comparisons for each laboratory parameter will be based on 3-by-3 tables (shift tables) that compare the baseline LNH classification to the LNH classification at each postbaseline visit and at the end of treatment. Similar shift tables will also compare the baseline LNH classification to the LNH classification for the highest and lowest value during the treatment period.

[Appendix 1](#) (Sponsor's Grading for Laboratory Values) presents the criteria that will be used to identify subjects with treatment-emergent markedly abnormal laboratory values (TEMAV). Except for phosphate, a TEMAV is defined as a postbaseline value with an increase from baseline to a grade of 2 or higher. For phosphate, a TEMAV was defined as a postbaseline value with an increase from baseline to a grade of 3 or higher. When displaying the incidence of TEMAVs, each subject may be counted once in the laboratory parameter high and in the laboratory parameter low categories, as applicable.

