Glucose, serum-low (hypoglycemia)	<LLN – 55 mg/dL <LLN – 3.0 mmol/L	<55 – 40 mg/dL <3.0 – 2.2 mmol/L	<40 – 30 mg/dL <2.2 – 1.7 mmol/L	<30 mg/dL <1.7 mmol/L life-threatening consequences; seizures

Sponsor's Grading for Laboratory Values				
	Grade 1	Grade 2	Grade 3	Grade 4
Phosphate, serum-low (hypophosphatemia)	<LLN – 2.5 mg/dL <LLN – 0.8 mmol/L	<2.5 – 2.0 mg/dL <0.8 – 0.6 mmol/L	<2.0 – 1.0 mg/dL <0.6 – 0.3 mmol/L	<1.0 mg/dL <0.3 mmol/L life-threatening consequences
Potassium, serum-high (hyperkalemia)	>ULN – 5.5 mmol/L	>5.5 – 6.0 mmol/L	>6.0 – 7.0 mmol/L hospitalization indicated	>7.0 mmol/L life-threatening consequences
Potassium, serum-low (hypokalemia)	<LLN – 3.0 mmol/L	<LLN – 3.0 mmol/L; symptomatic; intervention indicated	<3.0 – 2.5 mmol/L hospitalization indicated	<2.5 mmol/L life-threatening consequences
Sodium, serum-high (hypernatremia)	>ULN – 150 mmol/L	>150 – 155 mmol/L	>155 – 160 mmol/L hospitalization indicated	>160 mmol/L life-threatening consequences
Sodium, serum-low (hyponatremia)	<LLN – 130 mmol/L	N/A	<130 – 120 mmol/L	<120 mmol/L life-threatening consequences
Triglyceride, serum-high (hypertriglyceridemia)	150 – 300 mg/dL 1.71 – 3.42 mmol/L	>300 – 500 mg/dL >3.42 – 5.7 mmol/L	>500 – 1000 mg/dL >5.7 – 11.4 mmol/L	>1000 mg/dL >11.4 mmol/L life-threatening consequences
Uric acid, serum-high (hyperuricemia)	>ULN – 10 mg/dL ≤0.59 mmol/L without physiologic consequences	N/A	>ULN – 10 mg/dL ≤0.59 mmol/L with physiologic consequences	>10 mg/dL >0.59 mmol/L life-threatening consequences

ALT = alanine aminotransferase (serum glutamic pyruvic transaminase), AST = aspartate aminotransferase (serum glutamic oxaloacetic transaminase), GGT = γ -glutamyl transpeptidase, N/A = not applicable, LLN = lower limit of normal, ULN = upper limit of normal, WBC = white blood cell.

Based on Common Terminology Criteria for Adverse events (CTCAE) Version 4.0. Published: May 28, 2009 (v4.03: June 14, 2010).

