Glucose, serum-high (hyperglycemia)	Fasting glucose value: >ULN – 160 mg/dL >ULN – 8.9 mmol/L	Fasting glucose value: >160 – 250 mg/dL >8.9 – 13.9 mmol/L	>250 – 500 mg/dL; >13.9 – 27.8 mmol/L; hospitalization indicated	>500 mg/dL; >27.8 mmol/L; life-threatening

Sponsor's Grading for Laboratory Values

	Grade 1	Grade 2	Grade 3	Grade 4
				consequences
Glucose, serum-low (hypoglycemia)	<LLN – 55 mg/dL <LLN – 3.0 mmol/L	<55 – 40 mg/dL <3.0 – 2.2 mmol/L	<40 – 30 mg/dL <2.2 – 1.7 mmol/L	<30 mg/dL <1.7 mmol/L life-threatening consequences; seizures
Phosphate, serum-low (hypophosphatemia)	<LLN – 2.5 mg/dL <LLN – 0.8 mmol/L	<2.5 – 2.0 mg/dL <0.8 – 0.6 mmol/L	<2.0 – 1.0 mg/dL <0.6 – 0.3 mmol/L	<1.0 mg/dL <0.3 mmol/L life-threatening consequences
Potassium, serum-high (hyperkalemia)	>ULN – 5.5 mmol/L	>5.5 – 6.0 mmol/L	>6.0 – 7.0 mmol/L hospitalization indicated	>7.0 mmol/L life-threatening consequences
Potassium, serum-low (hypokalemia)	<LLN – 3.0 mmol/L	<LLN – 3.0 mmol/L; symptomatic; intervention indicated	<3.0 – 2.5 mmol/L hospitalization indicated	<2.5 mmol/L life-threatening consequences
Sodium, serum-high (hyponatremia)	>ULN – 150 mmol/L	>150 – 155 mmol/L	>155 – 160 mmol/L hospitalization indicated	>160 mmol/L life-threatening consequences
Sodium, serum-low (hyponatremia)	<LLN – 130 mmol/L	N/A	<130 – 120 mmol/L	<120 mmol/L life-threatening consequences
Triglyceride, serum-high (hypertriglyceridemia)	150 – 300 mg/dL 1.71 – 3.42 mmol/L	>300 – 500 mg/dL >3.42 – 5.7 mmol/L	>500 – 1000 mg/dL >5.7 – 11.4 mmol/L	>1000 mg/dL >11.4 mmol/L life-threatening consequences
Uric acid, serum-high (hyperuricemia)	>ULN – 10 mg/dL ≤0.59 mmol/L without physiologic consequences	N/A	>ULN – 10 mg/dL ≤0.59 mmol/L with physiologic consequences	>10 mg/dL >0.59 mmol/L life-threatening consequences

Based on Common Terminology Criteria for Adverse events (CTCAE) Version 4.0. Published: 28 May 2009 (v4.03: 14 Jun, 2010).

ALT = alanine aminotransferase (serum glutamic pyruvic transaminase), AST = aspartate aminotransferase (serum glutamic oxaloacetic transaminase), GGT = γ -glutamyl transpeptidase, , LLN = lower limit of normal, N/A = not applicable, ULN = upper limit of normal, WBC = white blood cell.

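### For low sodium and high uric acid, the SAP's Grade 1 fallback counts new mild shifts as markedly abnormal, which the protocol's rule does not, and the SAP does not declare the change

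*SAP*

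**What the plan says.** Protocol section 9.7.1.8.3 gives the rule for treatment-emergent markedly abnormal values (TEMAVs): "Except for phosphate, a TEMAV is defined as a postbaseline value with an increase from baseline to a grade of 2 or higher". Its single exception is stricter: "For phosphate, a TEMAV was defined as a postbaseline value with an increase from baseline to a grade of 3 or higher". It says nothing about falling back to Grade 1.

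SAP section 5.6.2 starts from the same threshold, Grade 2 and above, in the sentence that begins: "A laboratory test will be considered markedly abnormal if the result worsens to meet Eisai grading criteria for laboratory values limit of Grade 2 or". The section then adds the fallback: "If the Grade 2 limit is missing, the Grade 1 limit will be considered". It separately defines an abnormal value as one outside the reference range, and plans shift tables of low, normal and high classifications from baseline to the end-of-study or early-termination visit.

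SAP Appendix 13.1 states that its grading table is taken from protocol Appendix 1. SAP section 7, which is reserved for changes to the planned analyses, reads only: not applicable.

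**The concern.** The two documents grade with the same table but apply different rules to it. Where no Grade 2 limit exists, the protocol's threshold is met only at the next defined grade above, whereas the SAP drops to the grade below. For the rows concerned, that grade begins at the edge of the reference range. A value that the SAP elsewhere calls merely abnormal then enters the table of markedly abnormal values, beside analytes held to Grade 2. A reader of the table would not know that two analytes follow a looser standard, or that it departs from the protocol. At stake is the meaning of one descriptive safety table in each cohort. The primary analyses of SpO₂ and the apnea-hypopnea index (AHI) are not involved.

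**Working it through.** There is no stated figure to reproduce, so the check has two parts: where the rules differ, and how many extra flags chance could produce.

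**1. Rows that the fallback reaches.** Reading down the Grade 2 column in protocol Appendix 1 and SAP Appendix 13.1, exactly two cells are marked N/A: low sodium and high uric acid. Both analytes are in the laboratory panel (protocol Table 4). The SAP also drops the phosphate exception, but phosphate is not in that panel, so nothing follows from it.

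**2. The two rules applied to those rows.**

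| Analyte | Grade 1 | Lowest grade meeting the protocol rule | Band counted by the SAP only |
|---|---|---|---|
| Low sodium | "<LLN – 130 mmol/L" | Grade 3: "<130 – 120 mmol/L" | New worsening to below LLN, down to 130 mmol/L |
| High uric acid | ">ULN – 10 mg/dL ≤0.59 mmol/L without physiologic consequences" | Grade 3: same numeric range, but with physiologic consequences | New worsening to above ULN, up to 10 mg/dL, without consequences |

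The documents give no reference limits, so test values need assumed ones.

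- Sodium, LLN taken as 133, 135 or 137 mmol/L: 131 mmol/L is flagged by the SAP only; 129 and 119 are flagged by both rules.
- Uric acid, ULN taken as 6, 7 or 8 mg/dL: 9.9 mg/dL without consequences is flagged by the SAP only; 10.1 mg/dL, read on its numeric limit, is flagged by both.

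**3. Chance flags.** The SAP requires worsening, so only subjects inside the limit at baseline and beyond it afterwards count. Let q be the share of values beyond the limit and ρ the within-subject correlation, with one post-baseline sample and bivariate normal values (all assumptions). With c the standard normal quantile at 1 − q:

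- P(beyond at both times) = 1 − 2(1 − q) + Φ₂(c, c; ρ)
- P(new shift) = q − P(beyond at both times)

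For q = 0.025:

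- ρ = 0.5: 0.025 − 0.0046 = 0.0204
- ρ = 0.8: 0.025 − 0.0110 = 0.0140

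Expected flags are n × P(new shift), and the probability of at least one is 1 − (1 − P)ⁿ:

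| Cohort | Expected per analyte, ρ = 0.8 to 0.5 | Probability of at least one |
|---|---|---|
| OSA, n = 30 | 30 × 0.0140 = 0.42 to 30 × 0.0204 = 0.61 | 0.35 to 0.46 |
| Healthy volunteers, n = 12 | 12 × 0.0140 = 0.17 to 12 × 0.0204 = 0.24 | 0.16 to 0.22 |

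The result depends on q. At q = 0.10, P(new shift) is 0.0438 (ρ = 0.8) to 0.0676 (ρ = 0.5). That gives 1.31 to 2.03 expected flags in the OSA cohort and 0.53 to 0.81 in healthy volunteers.

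**4. Other rows with the same difficulty.** Uric acid Grades 1 and 3 cover one numeric range and differ only by physiologic consequences. Low potassium Grades 1 and 2 likewise share one range, with Grade 2 adding symptoms and a need for intervention. Neither document says how these conditions enter the flag.

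**The case against.** The strongest reply is that the practical effect is close to nil. Protocol Tables 5 and 6 schedule laboratory tests only at screening, baseline and end of study or early termination. For completers, the post-baseline sample comes 14 to 21 days after the last dose and after every treatment period, so it separates treatments poorly whichever limit is used. The table feeds no decision rule, and the same excursions appear in the shift tables. This stands, and it is why the point is minor.

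A second reply is that the protocol leaves detail to the SAP and does not address rows without a Grade 2 limit, so a more sensitive flag in a safety study is a fair choice. This mitigates but does not rebut: Grade 3 satisfies a rule of Grade 2 or higher, Grade 1 does not, and the choice is undeclared. The SAP cites a protocol version 8.0 of 11 December 2017, while the protocol at hand is v2.0 of 12 March 2018. The latter's revision history lists no change to section 9.7.1.8.3, so nothing suggests that the definition once differed.

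Three stronger readings are tempting and not supported:

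- A reader might infer that any sodium below normal or uric acid above normal is flagged. The SAP requires a result that worsens to the limit, so a subject already beyond it at baseline who does not worsen is not counted.
- A reader might multiply all 42 planned completers by 2.5% and expect 42 × 0.025 = 1.05 false flags per analyte. That ignores the worsening condition and pools cohorts that the SAP analyses separately.
- A reader might think that moving uric acid to Grade 3 settles the matter. Programmed on values alone, Grade 3 gives the same flag as Grade 1.

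**Conclusion.** The contradiction is real and limited. The SAP's fallback departs from the protocol's definition for two analytes, and section 7 does not record it. For low sodium the difference is clear on values alone: the flag moves from below 130 mmol/L to a new shift below LLN. For uric acid the rules also differ, but the difference turns on a clinical condition that neither document says how to record.

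Under the 2.5% assumption, chance adds fewer than one flag per analyte in either cohort. That size rests on assumed reference ranges, correlation and a single post-baseline sample; a larger share beyond the limit raises it. One descriptive table per cohort is affected. This is a minor correction worth making, and it has no bearing on the trial's primary conclusions.

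**What to change.** Delete the fallback sentence from SAP section 5.6.2 and apply the protocol rule, so that low sodium is flagged at Grade 3 or higher. Grade 1 shifts stay visible in the low-normal-high shift tables.

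Add one sentence on how grade conditions that are not numeric enter the flag, naming uric acid (Grades 1 and 3) and low potassium (Grades 1 and 2). Without it, the flag for those rows cannot be programmed unambiguously under either rule.

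If the sponsor prefers to keep the fallback, declare it in SAP section 7 and label the two rows as based on Grade 1.

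The cost is one or two SAP sentences and a small change to the sodium flag. Uric acid and potassium also need a decision on whether the clinical condition is captured or ignored. The SAP introduction allows documented updates approved before unblinding.
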